4.2.3 Safety Endpoints

The safety endpoints of the study are:

- Incidence of adverse events and serious adverse events not due to underlying disease;
- Incidence of abnormal findings in clinical safety laboratory parameters, vital signs, and ECGs.

4.2.4 Exploratory Endpoints

The exploratory endpoints of the study are:

- Percentage of participants who report Long COVID symptoms
- Total score on the Patient Health Questionnaire-9 (PHQ-9)
- Total and subscale scores on Long COVID Questionnaire (LCQ)
- Total and subscale scores on Long COVID Informant Questionnaire (LCIQ)

4.3 Clinical Trial Committees

A Data Monitoring Committee (DMC) will be established. The DMC will assess ongoing safety at pre-specified timepoints as detailed in the DMC Charter. The DMC will also review unblinded efficacy data at the time of the interim analysis. An independent unblinded statistician who is not involved in the study conduct will provide safety and efficacy data to the DMC for review.

DMC membership, scope and frequency of safety reviews will be described in the DMC Charter.

4.4 Completion of Clinical Trial

A participant is considered to have completed the clinical trial if he/she has completed the Day 40 assessments as shown in [Table 3](#) - SOA.

The end of the clinical trial is defined as the date of last scheduled procedure shown in the SOA for the last participant in the trial.

5 STUDY ENROLMENT AND WITHDRAWAL

5.1 Inclusion Criteria

To be eligible for study entry, participants must satisfy all of the following criteria at Screening:

1. Have one or more of the following comorbidities:
 - a. Age \geq 65 years;
 - b. Obesity (BMI \geq 30);
 - c. Hypertension (on one or more drugs for treatment of hypertension);
 - d. Diabetes (on one or more drugs for Type I or Type II diabetes);
 - e. Cardiovascular disease (on one or more drugs for treatment of cardiovascular disease, other than aspirin);
 - f. History of congestive heart failure (CHF) or myocardial infarction (MI);
 - g. Black or African-American race (at least one parent identifies as Black or African-American);
 - h. Hispanic or Latino ethnicity.
2. Have a positive COVID-19 test in the last 28 days;
3. Have room air SaO₂ <96%, or SpO₂ < 96% on room air at sea level, or PaO₂/FiO₂ < 300;
4. Have abnormal chest X-ray, MRI or CT scan consistent with pulmonary complications from COVID-19;
5. Provide written informed consent prior to any study related procedures being performed.

5.2 Exclusion Criteria

Participants will be excluded from the study if 1 or more of the following criteria are applicable at Screening:

1. Age < 18 years;
2. Require immediate intubation due to advanced respiratory failure – including CPAP and BIPAP;
3. Require immediate admission to an ICU for any reason;
4. On therapy with approved TNF inhibitor (eg: infliximab, etanercept, adalimumab, certolizumab pegol, golimumab, thalidomide, etc) in the last 6 months;
5. Being treated with dexamethasone (IV or PO) at a dose of >15mg per day or solumedrol or equivalent corticosteroid at a dose of >120mg per day;
6. Taking any medication known to be CCR5 receptor antagonist (eg: leronlimab, aplaviroc, vicriviroc or maraviroc) in the last 6 months;
7. Taking any medication known to inhibit the cytokine pathway (eg: anakinra, tocilizumab, siltuximab, etc) in the last 6 months;
8. Known to be pregnant;
9. Has known HIV, HCV or HBV infection;
10. Has known Mycobacterium tuberculosis infection or evidence of infection on chest X-ray;
11. Significant hepatic disease (ALT/AST > 4 times the ULN);
12. On therapy for cancer in the last 6 months;
13. On therapy for organ transplant in the last 6 months or on a waiting list for organ transplant, including patients on renal replacement therapy for any reason;
14. Known hypersensitivity to investigational product or its excipients;
15. Participating in an investigational drug or device trial;
16. Congestive heart failure (CHF) or myocardial infarction (MI) diagnosed in the last 2 months.

5.3 Reasons for Withdrawal or Termination

- A participant may withdraw from the clinical trial at any time at his/her own request.

- The investigator also has the right to withdraw the participant from the study for loss to follow-up.

The reason for study discontinuation will be recorded on the CRF.

5.4 Handling of Withdrawal or Termination

Participants withdrawing from the study will be encouraged to complete the same final evaluations as participants completing the study according to this protocol (Day 40 assessments).

Reasonable efforts will be made to contact participants who are lost to follow-up. Investigator will be expected to try as much as possible to re-connect those participants at the end of the trial in order to obtain at least their vital status. These efforts must be documented in the participant's file.

Investigators will be trained about the importance of participant retention and steps to prevent missing data.

5.5 Stopping Rules

Enrollment would be put on-hold and a DMC meeting would be convened within 48 hours if any of the following is reported:

1. Death in any participant in which the cause of death is judged to be possibly related or related to the study drug by the treating investigator;
2. The occurrence in any participant of a life-threatening SAE whose causal relationship to study drug is judged to be possibly related or related by the treating investigator;
3. Two (2) occurrences of Grade 3 or higher toxicities that are assessed to be related to the study drug by investigator;
4. Two (2) occurrences of a clinically significant Grade 3 or higher laboratory abnormality assessed to be related to the study drug by investigator.

After review of the case(s), the DMC would make a recommendation to the Sponsor concerning continuation or stopping of the trial.

Additionally, the DMC will review the safety data throughout the study and unblinded SAEs and SUSARs (not meeting criteria 1 or 2 above) will be forwarded to the DMC for review within 48 hours of the event being reported to the sponsor. The DMC may recommend at any time that the trial stop based on safety concerns.

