5.6 Premature Termination or Temporary Suspension of Study

This study or the study site may be temporarily suspended or prematurely terminated if there is sufficient reasonable cause. Study enrolment may be temporarily suspended if the DMC considers that the number and/or severity of adverse events justify suspension of the study. Written notification, documenting the reason for study suspension or termination will be provided by the suspending or terminating party to the investigator, and regulatory authorities.

If the study or the study site is prematurely terminated or suspended, the investigator will promptly inform the HREC/IRB and will provide the reason(s) for the termination or suspension.

Circumstances that may warrant termination or suspension include, but are not limited to:

- Failure of the investigator to comply with the protocol, the requirements of the HREC/IRB, or local health authorities, the sponsor's procedures, or GCP guidelines;
- Inadequate recruitment of participants by the investigator;
- The investigator (or delegate) and the sponsor consider that the number and/or severity of adverse events justify discontinuation of the study;
- The Sponsor makes a unilateral request to do so.

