6.3 Dosing and Administration

All randomized participants will receive either INB03 1mg/kg (not to exceed 90 mg) by SC injection or Placebo by SC injection immediately upon randomization (Study Day 1). A second dose of study drug will be administered on Study Day 8, if participant remains in hospital.

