8 STUDY SCHEDULE OF ASSESSMENTS

The Schedule of Assessments is provided in [Table 3](#).

[illegible]

Abbreviations: AE = Adverse Event, ECG = electrocardiogram, MRI = magnetic resonance imaging.

1. Can be same as Day 1.
2. Every attempt should be made to conduct the Day 28 Visit (+3d) and the Day 40 Visit (± 2 d) on site to ensure collection of all study safety assessments. Remote conduct of the Day 28 and Day 40 Visits (i.e. via Telehealth) will be considered by the sponsor on a case by case basis.
3. The vital signs should be taken at approximately the same time each day, preferably between 12pm-5pm.
4. Data for all routine 12-lead ECGs performed while the participant is an inpatient will be captured on the CRF. Additionally, the Day 28 and Day 40 12-lead ECG can be omitted if this visit is conducted remotely.
5. Testing for COVID-19 needs to have been performed and a positive result obtained within 28 days of Screening.

6. If laboratory evaluations are performed more than once a day as part of the routine management of hospitalized COVID-19 patients, the results from the first set of daily labs collected will be reviewed for this study and entered in the CRF. Safety clinical laboratory samples will be analysed by the investigational site's local pathology laboratory.
7. Pregnancy test (urine or serum) will be performed for women of childbearing potential at screening.
8. Blood sample to check TNF levels will be collected prior to dosing with study drug on Day 1. This lab will be analysed at the investigational site's local pathology laboratory.
9. Blood sample to perform anti-drug antibody (ADA) test will be collected prior to dosing with study drug on Day 1. ADA samples will also be collected at Day 28 and Day 40. This lab will be collected at the site and shipped to the central laboratory for analysis.
10. The second dose of study drug will be administered on Day 8, if participant is still in hospital.
11. The Screening WHO Ordinal Scale will be completed any time after informed consent and up to 1-hour post-randomization on Day 1. The scale will then be completed daily during the afternoon hospital rounds until participants are discharged from hospital. The scale will also be collected on Day 28 and Day 40.
12. Participants will be assessed for development of disease progression from randomization to Study Day 40.
13. Concomitant medications and AEs will be recorded for all participants who are randomized until Study Day 70.

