6.1.6 Study Drug Exposure and Compliance

Patients randomized to study treatment are to receive their first dose on Day 1 and a second dose on Day 8. All effort will be made for patients who remain in the hospital on Day 8 to receive their second dose of study treatment. If the patient is discharged prior to Day 8, no second dose will be administered.

Compliance will not be assessed in this study as sites are administering study treatment. As the disease in nature may progress quickly, the expectation is that at least 1 dose of study treatment will be given.

The number and percentage of patients who receive 1 dose and 2 doses will be summarized by treatment arm and overall. The planned dose level and total dose administered will be descriptively summarized by dose received.

Study treatment administration details, including reasons for not administering drug and if there were issues with the administration will be listed.

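### The safety stopping rule holds enrolment automatically but not dosing, so pending Day 8 doses stay due during review of a suspected drug-related death or life-threatening event unless someone uses discretion

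*Protocol*

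**What the plan says.** Protocol 5.5 lists four triggers: one death judged possibly related or related to study drug, one life-threatening SAE so judged, two related toxicities of Grade 3 or higher, and two related, clinically significant laboratory abnormalities of Grade 3 or higher. The consequence is the same for all four: "Enrollment would be put on-hold and a DMC meeting would be convened within 48 hours if any of the following is reported". The second trigger reads "The occurrence in any participant of a life-threatening SAE whose causal relationship to study drug is judged to be possibly related or related", an assessment made by the treating investigator. After its review the DMC makes a recommendation to the sponsor. The 48 hours is the time to convene; no deadline is given for the recommendation.

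The DMC sentence in 5.6 is also confined to enrolment: "Study enrolment may be temporarily suspended if the DMC considers that the number and/or severity of adverse events justify suspension of the study".

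On dosing, Protocol 6.3 says "A second dose of study drug will be administered on Study Day 8, if participant remains in hospital". Table 1 repeats that condition, and footnote 10 of the Schedule of Assessments says "The second dose of study drug will be administered on Day 8, if participant is still in hospital". None of the three makes an exception for a safety hold. SAP 6.1.6 adds "All effort will be made for patients who remain in the hospital on Day 8 to receive their second dose of study treatment".

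Wider powers exist. Section 5.5 says "The DMC may recommend at any time that the trial stop based on safety concerns", and 5.6 opens with "This study or the study site may be temporarily suspended or prematurely terminated if there is sufficient reasonable cause".

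**The concern.** A hold on a suspected drug-related death or life-threatening event is meant to limit exposure while causality is unsettled. In a single-dose trial an enrolment hold does that completely. Here there is a second dose a week later, and an enrolment hold does not reach inpatients who are waiting for it.

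The stated condition also tends to select the wrong people. A participant who survives a life-threatening, possibly related event after dose 1 may well still be in hospital on Day 8, and so meets the one condition for a second dose.

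What is at stake is participant safety, not the analysis. Section 2.4 calls this the first study of INB03 in pulmonary complications of COVID-19. Section 2.5 reports the dose in more than nine people, with one injection-site inflammation and otherwise good tolerability for up to 117 days. That is some reassurance on repeat dosing, but from few people.

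**Working it through.** The plan gives no figure to reproduce. The check is a comparison of texts, followed by an illustration of size.

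**Step 1: can anything stop a pending dose 2 when a 5.5 trigger is met?**

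| Route | What it does | Automatic on a trigger? |
|---|---|---|
| 5.5 hold | Stops enrolment | Yes, but dosing is not mentioned |
| 5.5 DMC advice | DMC may recommend stopping; the sponsor decides (SAP 3.4) | No |
| 5.6 DMC sentence | Enrolment may be suspended | No, and enrolment only |
| 5.6 opening sentence | Study or site may be suspended or terminated | No |
| 6.4.2 unblinding | Ends treatment, but only for the unblinded participant | No; the decision to unblind is discretionary |
| 10.2 immediate-hazard exception | Change allowed before approval | No |
| 10.3 safety deviation | Site may deviate at once | No |
| 5.3 withdrawal | Participant's own request; the investigator's stated ground is loss to follow-up | No |

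The only automatic measure does not reach dosing, and no measure that can stop a dose is automatic.

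**Step 2: how many active doses could be involved?** The documents give neither the accrual rate, nor the share in hospital on Day 8, nor the chance that a hold occurs. The figures below are conditional on a hold and use assumed inputs. Randomisation is 1:1 (Protocol 6.4.3), and dose 2 falls 7 days after randomisation (Protocol 4.1).

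Active doses due = 0.5 × (weekly accrual ÷ 7) × min(days of hold, 7) × share in hospital on Day 8

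The limit of 7 days applies because enrolment is held: once everyone randomised in the previous week has passed Day 8, no further second dose falls due. The chance of at least one active dose is 1 − exp(−doses due), treating the count as Poisson.

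- Set A, low: 2 per week, 30%, 2 days. 0.5 × 2/7 × 2 × 0.30 = 0.086; chance 8.2%. Limit 0.5 × 2 × 0.30 = 0.3.
- Set A, high: 10 per week, 60%. 0.5 × 10/7 × 2 × 0.60 = 0.857; chance 57.6%. Limit 3.0.
- Set B, low: 3.5 per week, 20%. 0.5 × 3.5/7 × 2 × 0.20 = 0.10; chance 9.5%. Limit 0.35.
- Set B, high: 14 per week, 50%. 0.5 × 14/7 × 2 × 0.50 = 1.00; chance 63.2%. Limit 3.5.
- Set C, low: the 79 randomised (SAP 6.2.4) over an assumed 40 weeks is 79/40 = 1.98 per week; with 30%, 0.085; chance 8.1%. Limit 0.30.
- Set C, high: 79 over an assumed 20 weeks is 3.95 per week; with 60%, 0.339; chance 28.7%. Limit 1.19.

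Across the sets this is about 0.1 to 1 active doses in 48 hours and 0.3 to 3.5 per hold, however long the review takes. Both arms together are twice that: 0.6 to 7 doses per hold.

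**The case against.** The strongest reply is that nobody is compelled to give a dose during a review. The sponsor can suspend the study at once under 5.6, the site can deviate at once under 10.3, 10.2 exempts changes needed to remove an immediate hazard, and 2.4 promises anaphylaxis precautions at administration. SAEs reach the sponsor within 24 hours (7.1.9.6). SAP 6.1.6 lists reasons for not giving drug, so a missed dose is foreseen. All of this stands. A reader might infer that the plan obliges staff to dose through a hold, or leaves no means of stopping; the documents do not support that. They support only that stopping depends on someone choosing to act, while the enrolment hold does not. Anaphylaxis precautions manage a reaction but do not bar re-dosing someone who has reacted.

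A reader might also take SAP 6.1.6 as an instruction to dose regardless. It sits in a section on summarising exposure, not in dosing instructions, and carries little weight here.

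The size is open to challenge. The upper accrual rates of 10 and 14 per week would have produced the 79 randomised in about 8 weeks (79/10 = 7.9) and 6 weeks (79/14 = 5.6). Set C, itself based on an assumed duration, gives only 0.1 to 0.3 active doses in 48 hours. Those doses go to people who have already had dose 1; new first exposures are blocked. This too stands, and it rules out any reading that many participants would be exposed.

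Holds could also be frequent. Under 7.1.9.4, possibly related includes events that the participant's clinical state could have caused, so in a sick population disease alone might trigger a hold. That is a real cost of a dosing hold.

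Finally, the DMC charter and Pharmacy Manual were not available. Either might contain a dosing hold; only its absence from the protocol and SAP can be shown.

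**Conclusion.** The point holds as a gap in the written rule. The automatic hold in 5.5 and the DMC sentence in 5.6 stop at enrolment, and the dosing sections state a single condition for dose 2. Followed literally, the plan leaves second doses due while a possibly drug-related death or life-threatening event is under review, including for a survivor of that event.

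The effect is small, and its size rests wholly on the assumed accrual and inpatient share. The case for change is that each such dose is easily avoided, not that there are many. It is a cheap improvement to safety wording and does not affect the validity of the primary analysis. There is no live exposure to prevent: enrolment ended on 15 June 2021 and SAP 6.2.4 says those randomised were followed to completion. The value lies in a restart or a successor protocol.

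The lack of a hypersensitivity check before dose 2 (exclusion 14 applies at Screening only, although 2.4 expects that allergic reactions may occur) is a separate matter of individual dosing criteria. It adds no weight to the point about the stopping rule.

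**What to change.** In 5.5, and in the DMC sentence of 5.6, extend the hold to *enrolment and all study drug dosing, including pending Day 8 doses, until the DMC has made its recommendation and the sponsor has decided*. Running it to the sponsor's decision matters: the DMC only recommends, so a hold ending at the recommendation could lapse just after advice to stop. State also that a Day 8 dose missed because of a hold is not given later, or give a fixed window for it. If the charter already holds dosing, 5.5 should say so.

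As a separate change, in 6.3 and Table 1 withhold dose 2 from a participant who, after dose 1, had a life-threatening event judged possibly related or related, or a hypersensitivity reaction; the protocol should define the latter. This bar should not extend to every possibly related event of Grade 3 or higher, because that category admits disease-caused events and could remove dose 2 from many sick inpatients.

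The cost is a few sentences and some missed second doses: at most about 0.6 to 7 per hold in both arms together under the assumptions above, times a number of holds that cannot be derived, plus those withheld individually. The hold applies to both arms without unblinding. The primary estimand in SAP 6.2.1.1 already handles a missed dose 2 by treatment policy, so the analysis need not change. SAP 6.1.6 needs no change for safety.

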5.6 Premature Termination or Temporary Suspension of Study

This study or the study site may be temporarily suspended or prematurely terminated if there is sufficient reasonable cause. Study enrolment may be temporarily suspended if the DMC considers that the number and/or severity of adverse events justify suspension of the study. Written notification, documenting the reason for study suspension or termination will be provided by the suspending or terminating party to the investigator, and regulatory authorities.

If the study or the study site is prematurely terminated or suspended, the investigator will promptly inform the HREC/IRB and will provide the reason(s) for the termination or suspension.

Circumstances that may warrant termination or suspension include, but are not limited to:

- Failure of the investigator to comply with the protocol, the requirements of the HREC/IRB, or local health authorities, the sponsor's procedures, or GCP guidelines;
- Inadequate recruitment of participants by the investigator;
- The investigator (or delegate) and the sponsor consider that the number and/or severity of adverse events justify discontinuation of the study;
- The Sponsor makes a unilateral request to do so.

6 INVESTIGATIONAL PRODUCTS

6.1 Treatments Administered

The clinical trial will have two treatment arms INB03 + SOC or Placebo + SOC. Approximately 183 participants will be randomized to each arm. Participants randomized to the INB03 + SOC arm will receive INB03 1mg/kg up to a maximum of 90mg. Participants randomized to the Placebo + SOC will receive a SC injection of normal saline 0.01ml/kg up to a maximum of 0.9ml.

[Table 1](#) provides a summary of the investigational product to be administered in the study.

Table 1: Investigational Products Administered

Treatment	Dose form	Route of administration	Dose (mg)	Dose frequency
INB03	Liquid	SC injection	1mg/kg (not to exceed 90 mg)	1 st dose on Study Day 1 & 2 nd dose of Study Day 8 (if participant remains in hospital)
Placebo (Normal Saline)	Liquid	SC injection	0.01ml/kg (maximum of 0.9 ml)	

Abbreviations: SC=subcutaneous

6.2 Investigational Product Description

6.2.1 Formulation, Appearance, Packaging and Labelling

INB03

INB03 is a pegylated protein variant of sTNF, originally developed by Xencor Inc (United States Investigation New Drug 100,130) under the name XPro™ 1595. Refer to the INB03 IB for additional formulation and manufacturing specifics.

INB03 drug product is a liquid product supplied in single-use glass vials in a dose strength of 110 mg of drug. A 1.1 mL volume of drug product contains 100 mg/mL of INB03 and the following inactive ingredients: histidine, sodium chloride, and polysorbate 20 at pH 6.5.

The 100 mg/mL product vial is intended to deliver 1.0 mL of drug solution or 100 mg of INB03.

INB03 vials will be stored, labelled and distributed to the pharmacy of each study site by the Central Pharmacy. Prior to administration, INB03 will be prepared in syringes for SC injections as detailed in the Pharmacy Manual. The syringes will be labelled by pharmacy to maintain the blind.

Placebo

Placebo will be normal saline from the site pharmacy's stock. Saline is a clear liquid comparable in appearance to INB03. Prior to administration, Placebo will be prepared in syringes for SC injections as detailed in the Pharmacy Manual. The syringes will be labelled by pharmacy to maintain the blind.

